2. SYNOPSIS

Name of Sponsor/Company: Intercept Pharmaceuticals, Inc.
Name of Investigational Products: Obeticholic acid (OCA) and bezafibrate (BZF) in fixed-dose combination (FDC)
Name of Active Ingredient: Obeticholic acid (OCA); 6 α -ethyl-chenodeoxycholic acid; INT-747 Bezafibrate (BZF)
Title of Study: A Phase 3, Open-Label, Long-Term Safety Extension Study Evaluating the Safety and Tolerability of the Fixed-Dose Combination of Obeticholic Acid and Bezafibrate in Subjects with Primary Biliary Cholangitis
Investigators and/or Study Center(s): Approximately 60 investigational sites, globally
Studied Period: Actual date first subject enrolled: July 2024 Estimated date last subject completed: Q2 2029
Phase of Development: Phase 3
Objectives: Primary Objective: The primary objective is to assess the long-term safety and tolerability of the OCA + BZF FDC tablet (OCA 5 mg + BZF 400 mg sustained release [SR]) in subjects with primary biliary cholangitis (PBC). Efficacy Objectives: To assess the effects of the OCA + BZF FDC tablet in subjects with PBC on the following: 
Biochemical disease markers, including ALP, GGT, ALT, AST, and total and conjugated bilirubinALP <1.67x ULN, total bilirubin \leqULN, and ALP decrease of \geq15% from baselineNoninvasive assessments of liver fibrosis (transient elastography [TE], enhanced liver fibrosis [ELF] score)Disease severity scores (GLOBE, UK-PBC, and model of end-stage liver disease [MELD]) Exploratory Objectives: To assess the effects of the OCA + BZF FDC tablet in subjects with PBC on the following: 

[figure not shown]
– MELD score ≥ 15

**Methodology:**

Overview: This Phase 3, open-label, long-term safety extension (LTSE) study will evaluate the safety, tolerability, and efficacy of the OCA + BZF FDC tablet (OCA 5 mg + BZF 400 mg SR) in approximately 133 subjects with PBC for up to 60 months (5 years). Subjects from Study 747-213 or Study 747-214 will transition into Study 977-311 once Study 977-311 is active at their respective sites. The time subjects have spent in the LTSE phases in their respective studies, 747-213 or 747-214, will not count toward the 60 months in Study 977-311. Eligible subjects from other Sponsor studies may also transition to Study 977-311.

All subjects will transition in Study 977-311 to the OCA + BZF FDC tablet (OCA 5 mg + BZF 400 mg SR) and will receive investigational product once daily at the same time (AM dosing is preferred to align with all study visits) starting on Day 2. All subjects should continue their pre-study dose of ursodeoxycholic acid (UDCA) throughout study participation.

After the Day 1, Day 2, Month 1, Month 3, Month 6, and Month 12 visits, subsequent in-clinic study visits will occur every 6 months for the assessment of safety, tolerability, efficacy, PK, and PD.

Study Design Diagram

BZF=bezafibrate; D=day; EOS=end of study; FDC=fixed-dose combination; IP=investigational product; LTSE=long-term safety extension; M=month; OCA=obeticholic acid; SR=sustained release; UDCA=ursodeoxycholic acid

Notes: Subjects taking UDCA at the time of enrollment will remain on their stable dose of UDCA during the study.

Subjects will be re-consented.

Subjects in either Study 747-213 or Study 747-214 may already be in LTSE. The time subjects spent in LTSE on either study will not be carried over into this study, 977-311. Subjects will spend a total of 60 months (5 years) in Study 977-311.

^a The Day 2 Visit can be either a virtual or onsite visit. It will be scheduled on Day 2 to Day 7 of the study depending on when laboratory results are available and reviewed. Subjects can elect to pickup IP onsite (onsite Day 2 visit) or have it shipped directly to them (virtual Day 2 visit). For subjects that have IP shipped, the Day 2 virtual visit should be scheduled once the subject receives IP.

Number of Subjects (Planned):

Approximately 133 subjects

Diagnosis and Main Criteria for Inclusion:

1. All subjects with PBC who participated and are actively taking investigational product in Study 747-213 or Study 747-214 (or other Sponsor studies) are eligible to enroll in this study (977-311).
 - Subjects on a drug holiday within the previous 60 days due to unresolved treatment emergent adverse events (TEAEs) or serious adverse events (SAEs) in the parent study should discuss eligibility for rolling over to this study with the Sponsor Medical Monitor.
2. Contraception: Female subjects must be postmenopausal, surgically sterile, or, if premenopausal (and not surgically sterile), be prepared to use ≥ 1 highly effective method of contraception during the study and for at least 30 days after the last dose of investigational product. Highly effective methods of contraception per the Clinical Trials Facilitation and Coordination Group guidelines are those that alone or in combination results in a failure rate of less than 1% per year when used consistently and correctly. These highly effective contraception methods avoid the potential embryofetal risks from exposure to investigational medicinal products. Highly effective methods of contraception are as follows:
 - Intrauterine device
 - Intrauterine device
 - Intrauterine hormone-releasing system
 - Bilateral tubal occlusion

- Vasectomy (partner)
 - Combined (estrogen and progestogen containing) hormonal contraception (e.g., oral, intravaginal or transdermal) associated with inhibition of ovulation. If oral contraceptives are used, they must be used in combination with a male or female condom. Female subjects should have been on the hormone contraception for at least 8 days prior to Day 1 of their parent study.
 - Progestogen-only hormonal contraception (e.g., oral, injectable, or implantable) associated with inhibition of ovulation. If oral contraceptives are used, they must be used in combination with a male or female condom. Female subjects should have been on the hormone contraception for at least 8 days prior to Day 1 of their parent study.
 - Sexual abstinence, as a form of highly effective contraception if in line with the preferred and usual lifestyle of the subject, is defined as avoiding all types of sexual activity that could result in pregnancy during the entire period of the study treatment until at least 30 days after the last dose of investigational product. The reliability of sexual abstinence needs to be evaluated in relation to the duration of the clinical study.
3. Male subjects who are sexually active with female partners of childbearing potential must agree to use a condom with spermicide and to use (or have their partner use) 1 other approved method of highly effective contraception from the initiation of the study and until at least 90 days after the last dose of investigational product as listed in Inclusion Criterion #2.
 4. Male patients must refrain from sperm donation from the initiation of the study and until at least 90 days after the last dose of investigational product.
 5. Must provide written informed consent and agree to comply with the study protocol.

Key Exclusion Criteria:

1. Any history or presence in the last 30 days, before rolling over to this study, of other concomitant liver diseases, including any of the following:
 - Hepatitis C virus (HCV) infection with positive RNA
 - Active hepatitis B virus (HBV) infection; however, subjects who have seroconverted (hepatitis B surface antigen negative [sAg-], hepatitis B surface antibody positive [sAB+]; hepatitis B e-antigen negative [eAg-], hepatitis B e-antibody positive [eAb+]; HBV DNA negative) may be included in this study after consultation with the Medical Monitor and Sponsor Medical Monitor
 - Subjects should be excluded if positive HBV DNA or HCV RNA
 - Primary sclerosing cholangitis
 - Alcoholic liver disease
 - Definite autoimmune liver disease or PBC-autoimmune hepatitis (AIH) overlap
 - Metabolic dysfunction-associated steatohepatitis (MASH)
 - Gilbert's Syndrome (due to interpretability of bilirubin levels)
 - Rare liver conditions such as Wilson's disease, hemochromatosis, alpha-one anti-trypsin deficiency, or other conditions identified by the Principal Investigator
2. Clinical complications of PBC including:
 - Prior liver transplantation
3. Any history or presence in the last 30 days, before rolling over to this study, of any one of the following decompensating events:
 - Child-Pugh (CP) Score ≥ 7

- Clinical evidence of decompensated liver disease or evidence of portal hypertension, including but not limited to:
 - Varices (including a history of esophageal varix ligation or asymptomatic esophageal varices by endoscopy)
 - Ascites/hepatic hydrothorax
 - Spontaneous bacterial peritonitis
 - Hepatic encephalopathy
 - Jaundice (with total bilirubin >3 mg/dL [$>51.3 \mu\text{mol/L}$])
 - Biochemical evidence of hepatic impairment, decompensation, or injury including at least one of the following:
 - Total bilirubin >ULN
 - International normalized ratio (INR) >1.7
 - Albumin <3.5 g/dL
 - MELD >12
 - ALT >5x ULN
 - Known or suspected HCC
 - Prior trans-jugular intrahepatic portosystemic or peritoneovenous shunt procedure
 - Hepatorenal syndrome (type I or II) or serum creatinine >1.5 mg/dL (135 $\mu\text{mol/L}$) or estimated glomerular filtration rate (eGFR) <60 mL/min from the last lab assessment/visit in parent study, before transitioning to Study 977-311
 - Portopulmonary hypertension
 - Hepatopulmonary syndrome
4. Medical conditions that may cause non-hepatic increases in ALP (e.g., Paget's disease) or that may diminish life expectancy to <2 years, including known cancers (except carcinomas in situ or other stable, relatively benign conditions)
 5. Presence of any other disease or condition that interferes with the absorption, distribution, metabolism, or excretion of drugs including bile salt metabolism in the intestine (e.g., inflammatory bowel disease or gastric bypass procedure [gastric lap band is acceptable])
 6. Evidence or history of cholelithiasis or choledocholithiasis unless documented cholecystectomy. Gallbladder polyps if >5 mm in diameter
 7. History of chronic pancreatitis or recurrent acute pancreatitis – defined as at least 2 episodes of acute pancreatitis, with symptoms resolving between each episode
 8. History of drug-induced myopathy
 9. Chronic kidney disease (serum creatinine >1.5 mg/dL [$>135 \mu\text{mol/L}$]; creatinine clearance <60 mL/min) or undergoing dialysis
 10. Platelet count <150,000/ μL at the last visit in parent study, before transitioning to Study 977-311
 11. Known history of human immunodeficiency virus (HIV) infection
 12. History or presence of clinically concerning cardiac arrhythmias likely to affect survival during the study, QT interval of the electrocardiogram (QT) or QT interval of the electrocardiogram corrected (QTc) interval of >450 milliseconds for males and >470 milliseconds for females
 13. Severe pruritus or required systemic treatment for pruritus (e.g., with bile acid sequestrants [BAS] or rifampicin) within 2 months of Day 1 of Study 977-311. Subjects who plan to use or will use BAS during the study will not be eligible.

14. History of known or suspected clinically significant (CS) hypersensitivity to OCA, BZF, or other fibrates or any of their components
15. Known photoallergic or phototoxic reactions to fibrates
16. If female, known pregnancy, a positive urine pregnancy test (confirmed by a positive quantitative serum pregnancy test), or current lactation at the last visit in parent study, before transitioning to Study 977-311
17. Other CS medical conditions that are not well controlled or for which medication needs are anticipated to change during the study (e.g., Type 2 diabetes mellitus, hypothyroidism, nephritic or nephrotic syndrome, dysproteinemia, obstructive biliary disease, dyslipidemia), and/or up to the discretion of the Principal Investigator
18. Treatment with the following medications 30 days before Day 1 of Study 977-311, or plans to use these medications during the study: azathioprine, colchicine, cyclosporine, methotrexate, mycophenolate mofetil, pentoxifylline, rifampicin, statins, budesonide and other systemic corticosteroids (short-term use up to 2 weeks is permitted), monoamine oxidase inhibitors (MAOIs), and potentially hepatotoxic drugs (including α -methyl-dopa, sodium valproic acid, isoniazid, and nitrofurantoin)
19. Treatment with the following medications within 12 months before Day 1 of Study 977-311, or plans to use these medications during the study: antibodies or immunotherapy directed against interleukins or other cytokines or chemokines
20. Participation in a study of another investigational medicine or device within 30 days before Day 1 of Study 977-311 (except for Study 747-213, Study 747-214, or other eligible Sponsor study)
21. History of or ongoing alcohol or drug abuse within 1 year before Day 1 of Study 977-311. Subjects with moderate alcohol use within 3 months prior to the last visit in parent study, before transitioning to Study 977-311, will be excluded from this study. Moderate alcohol consumption is defined as 1 standard drink per day for women and 2 drinks per day for men; whereby 1 standard drink is equivalent to: 12 oz beer (5% alcohol), 5 ounces of wine (12% alcohol), or 1.5 ounces of 80 proof (40% alcohol)
22. History of noncompliance with medical regimens, or is considered by the Principal Investigator not able to meet the requirements as specified in the protocol from Day 1 throughout the duration of the study
23. Blood or plasma donation within 30 days before Day 1
24. Mental illness or other condition which may impair decision making, such that the validity of informed consent or ability to be compliant with the study is uncertain
25. A creatine kinase (CK) value on Day 1 of Study 977-311 $\geq 5 \times$ ULN or any abnormal laboratory value that is considered CS in the opinion of the Principal Investigator and Sponsor at the last visit in parent study, before transitioning to Study 977-311
26. Known or suspected nephrotic syndrome in the last 30 days, before rolling over to this study, based on the following diagnostic criteria (both Type 1 and Type 2):
 - Proteinuria, spot urine protein: albumin/creatinine ratio (ACR) of >300 mg/mmol (subjects with normal renal function and ACR values analyzed to be below the lower limits of detection are permitted)
 - Serum albumin <25 g/L
 - Clinical evidence of peripheral edema
 - Severe hyperlipidemia (total cholesterol above >10 mmol/L)

Hepatic and Renal Event Adjudication:

All events of potential hepatic injury, suspected liver-related clinical outcomes, and potential renal injury that occur after administration of the first dose of investigational product will be reviewed and adjudicated by independent and blinded adjudication committees, depending on event type.

Each adjudication committee has a charter that documents the reporting of events by the study site, definition of the potential events to be adjudicated, supply of source documentation to the committee, entire data flow and process from committee membership, review of the events by the committee, reporting of the final assessment, and the working procedures of the committee.

Specific details of the events that will be adjudicated are described in the respective adjudication charters. Any changes to either the adjudication process or changes to specific events to be adjudicated will be addressed in the charters and will be communicated to all study sites outside of a protocol amendment.

The adjudication committee members will include experts with relevant adjudication experience; they will not be involved in the study as Investigators, Data Monitoring Committee (DMC) members, or consultants. Any candidate found to have a conflict or whose name is listed on the Food and Drug Administration (FDA) debarment list will not be offered membership. Conflicts of interest are assessed regularly, and if members are found to have a new conflict of interest they will be replaced.

The adjudication of potential events will be based on available source documentation, including but not limited to individual clinical study data, hospital records, discharge summaries, and/or death certificates. The adjudication committees will not receive any individual subject treatment or site-specific information. All protected health information will remain confidential and will not be available to the adjudication committee. The assessment of events will be conducted in compliance with study-specific procedures, manuals, Good Clinical Practice (GCP), and all other applicable regulatory requirements, including the archiving of essential documents.

Investigational Products, Dosage, and Mode of Administration:

The single FDC tablet must be swallowed whole and not be chewed, divided, or crushed and must be taken with food and water (ad libitum) throughout the study period. Subjects are requested to take medication in the morning. Specific instructions for dosing will be provided for PK assessment days.

- FDC tablet (OCA 5 mg + BZF 400 mg SR), once daily

The FDC tablet will be dispensed in a bottle. Each subject should take 1 tablet daily. The FDC tablet will be provided for use only in this study and is not to be used for any other purpose. The Principal Investigator or designee will maintain a full record of investigational product accountability, including records of individual subject dispensing and final return or disposition (as directed by the Sponsor).

Duration of Treatment:

The total duration of Study 977-311 per subject will be a maximum of 60 months from day of study entry. The end of study is defined as the date of the last visit of the last subject.

Statistical Methods:**Analysis Populations:**

LTSE Population: The LTSE Population will include all subjects who receive at least 1 dose of the FDC tablet in Study 977-311.

Pharmacokinetic Population: The PK Population will include all subjects in LTSE Population who receive the FDC tablet in Study 977-311 and have a PK sample(s) without any major protocol deviations that could potentially affect plasma exposure.

Pharmacodynamic Population: The PD Population will include all subjects with a baseline assessment and at least 1 on-treatment assessment without any major protocol deviations that could potentially affect results.

Safety Analyses:

The LTSE Population will be the primary population used for safety analyses.

Safety data, including SAEs, TEAEs, physical examinations, electrocardiograms (ECGs), vital signs, clinical laboratory assessments, and treatment discontinuations, will be assessed.

The incidence of TEAEs and SAEs will be tabulated by system organ class, preferred term, and severity.

Laboratory parameters and vital signs will be summarized (including Hy's law) using descriptive statistics at baseline (defined as the last assessment performed before the first dose of investigational product in Study 977-311) and at each scheduled post-baseline visit in Study 977-311. The change from baseline will also be summarized. ECGs will be summarized using frequency at each visit. The shift from baseline will also be summarized.

[figure not shown]
Analyses of Efficacy and Exploratory Endpoints:

The LTSE Population will be the population used for the efficacy and exploratory analyses. Baseline is defined as the last assessment performed before the first dose of investigational product in Study 977-311, unless otherwise specified.

[figure not shown]
The efficacy endpoint at post-baseline site visits includes:

- Response rate of $\geq 40\%$ reduction from baseline and normalization rates of ALP
- Normalization rates of GGT, ALT, AST, total and conjugated bilirubin
- Change from baseline in GGT, ALT, ALP, AST, and total and conjugated bilirubin
- Percentage of subjects with ALP $< 1.67 \times \text{ULN}$, total bilirubin $\leq \text{ULN}$, and ALP decrease of $\geq 15\%$ from baseline
- Change from baseline in noninvasive markers of liver fibrosis, including liver stiffness measured by TE and ELF score
- Change from baseline in the GLOBE, UK-PBC, and MELD scores

The exploratory endpoints at post-baseline site visits include:

- MELD score ≥ 15

- Time to first occurrence of each individual component of the composite event endpoint.

All continuous and categorical efficacy and exploratory endpoints will be summarized using descriptive statistics at baseline and at each scheduled post-baseline visit.

Additional details regarding the planned analyses, methods, and outputs for the study will be included in the Statistical Analysis Plan (SAP).

PK, PD and PK/PD Analyses

The PK Population will be the primary population used for the PK analyses. The PD population will be the primary population for PD analyses. For PK/PD analyses, subjects in both the PK population and the PD population for the PD endpoint of interest will be included in the analysis. [REDACTED]

[REDACTED] will be summarized using descriptive statistics at each scheduled post-baseline visit.

Change from baseline and percent change from baseline in [REDACTED]

[REDACTED] will be calculated by timepoint and reported in individual listings and descriptive summary tables. PK/PD analyses may consist of scatter plots with correlation analysis and additional analyses if warranted by the data.

Sample Size Determination

This is an estimation study with no formal hypothesis to be tested. Therefore, sample size is strictly based on number of subjects being captured from studies 747-213 and 747-214, or other Sponsor studies. The sample size in this study is not calculated based on statistical consideration.

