5.4. Clinical Experience with Obeticholic Acid and Bezafibrate

The Sponsor has initiated a clinical development program to evaluate the safety and efficacy of BZF in combination with OCA in patients with PBC. The initial 4 studies include a Phase 1 study in healthy subjects (Study 747-123), a Phase 2 study (Study 747-213) in subjects with PBC that is being conducted globally (not including the US), a Phase 2 study (Study 747-214) being conducted globally (including the US) to evaluate the dose/exposure-response of the OCA + BZF combination and to provide further safety/tolerability information of the combination in the targeted population, and a Phase 1 absorption, metabolism, and excretion study of BZF (Study 977-113) in healthy subjects.

Study 747-123 is a completed, Phase 1, randomized, controlled study evaluating single-dose escalation of BZF given alone, multiple-dose escalation of OCA and BZF given alone and in combination, and the relative bioavailability of OCA and BZF administered in a fixed dose combination tablet compared to each product administered separately in healthy subjects. This study enrolled 132 healthy subjects.

Study 747-213 is an ongoing, Phase 2, double-blind, randomized, parallel group study evaluating the efficacy, safety and tolerability of OCA administered in combination with BZF in subjects with PBC who had an inadequate response or who were unable to tolerate UDCA. This study

has been fully enrolled (75 subjects), with a long-term safety extension (LTSE) currently ongoing. Subjects from Study 747-213 will transition into Study 977-311 once the study is active at their respective sites.

Study 747-214 is an ongoing, Phase 2a randomized, double-blind, active-control multicenter study, with an initial 3-month double blind treatment period, followed by a LTSE Period (up to 48 Weeks) being conducted in the US and non-US countries. The primary objective is to evaluate the efficacy, safety, and tolerability of OCA, administered alone or in combination with BZF, in subjects with PBC who had an inadequate response or who are unable to tolerate UDCA. This study has been fully enrolled (72 subjects), with an LTSE currently ongoing. Subjects from Study 747-214 will transition into Study 977-311 once the study is active at their respective sites.

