14.1.1.3. Treatment-Emergent Adverse Events

A TEAE is any event not present before the initiation of the investigational product in this study or any event already present, which worsens in either severity or frequency following exposure to the investigational product in this study.

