10.2.3. TEAE Analyses

All AE summaries will be restricted to TEAEs. Summaries that are displayed by SOC and PT will be ordered by descending order of incidence of system organ class and preferred term within each system organ class. Summaries of the following types will be presented:

- Overall summary of TEAEs
- Subject incidence of TEAEs and the total number of entries by MedDRA SOC and PT.
- Subject incidence of TEAEs by MedDRA SOC, PT, and highest severity. At each level of subject summarization, a subject is classified according to the highest

severity if the subject reported 1 or more events. AEs with missing severity will be considered severe for this summary.

- Subject incidence of TEAEs by MedDRA SOC, PT, and closest relationship to investigational product (Related/Not Related). Related AEs are those with relationships reported as “Definite,” “Probable,” or “Possible,” and unrelated AEs are those with relationships reported as “Unlikely” or “Not Related.” At each level of subject summarization, a subject is classified according to the closest relationship if the subject reported 1 or more events. AEs with a missing relationship will be considered related for this summary.
- Subject incidence of serious TEAEs and the total number of entries by MedDRA SOC and PT.
- Subject incidence of TEAEs leading to investigational product withdrawal or study discontinuation by MedDRA SOC and PT. This is a subset of the AEs where Action Taken with Study Treatment is checked as “Drug Withdrawn” or where “Subject Discontinued from Study” is checked.

The following listings will be presented by subject:

- All adverse events
- Serious adverse events (a subset of the AEs where serious is marked as “Yes”).
- Severe adverse events (a subset of AEs where severity is marked as “Severe”).
- Related adverse events (a subset of the AEs where relationship marked as “Definite,” “Probable,” or “Possible”).
- Adverse events leading to Study Drug Withdrawal or Study Discontinuation (a subset of the AEs where Action Taken with Study Treatment is checked as “Drug Withdrawn” or where “Subject Discontinued from Study” is checked).
- Adverse events leading to death.

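### A parent-study adverse event that is carried in and persists without worsening is absent from every AE summary table, including the table of events leading to withdrawal

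*Protocol*

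**What the plan says.** **Entry.** Inclusion criterion 1 (protocol synopsis, repeated in 8.2) addresses subjects on a drug holiday in the previous 60 days "due to unresolved treatment emergent adverse events (TEAEs) or serious adverse events (SAEs) in the parent study". They are not excluded outright; they "should discuss eligibility for rolling over to this study with the Sponsor Medical Monitor". Exclusion 13 removes severe pruritus and pruritus that needed systemic treatment within 2 months of Day 1. Other criteria remove bilirubin above ULN, ALT above 5x ULN and a history of drug-induced myopathy. No criterion bars a milder ongoing AE as such.

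**Parent treatment.** Protocol 5.4 describes Study 747-213 as "evaluating the efficacy, safety and tolerability of OCA administered in combination with BZF in subjects with PBC". Study 747-214 gives OCA alone or with BZF, and 5.4.3 shows placebo + BZF arms in both studies. Subjects from these studies have therefore been on OCA and/or BZF.

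**TEAE definition.** Protocol 14.1.1.3 covers events that are new in this study and "any event already present, which worsens in either severity or frequency following exposure to the investigational product in this study". SAP 10.2.1 keeps the worsening route but limits it to an increase in grade, during a Double-Blind period. It also counts an event with a missing start date that ends after first dose.

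**Tables.** SAP 10.2.3 states: "All AE summaries will be restricted to TEAEs". The table of events that end treatment is specified as "Subject incidence of TEAEs leading to investigational product withdrawal or study discontinuation by MedDRA SOC and PT". Protocol 15.3 and the synopsis are worded more widely: "The incidence of TEAEs and SAEs will be tabulated by system organ class, preferred term, and severity", with no treatment-emergent limit on SAEs.

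**The concern.** The primary objective is long-term safety and tolerability in subjects who have already been taking one or both components. For them, an event that continues on the FDC, or that finally makes them stop it, is a tolerability outcome in its own right. TEAE incidence is the right tool for new-onset risk. It cannot show persistence, because an event that does not worsen never enters the count.

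The withdrawal table matters most. A reader will take it as the number of subjects who stopped the FDC because of an adverse event. If some stopped for an event that began in the parent study, that number is too low, and it may not match the adverse-event reason in the disposition table.

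**Working it through.** The plan has no figure to reproduce: the sample size of about 133 is stated not to rest on a statistical calculation, and no count of events ongoing at entry is given. The check is therefore a trace of the rules, followed by a scale.

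**Step 1: a case that the protocol allows.** A subject enters with pruritus that began in the parent study on a known date. It is not severe and was not treated systemically in the previous 2 months, so exclusion 13 does not apply. On the FDC it stays at the same grade and frequency. Under protocol 14.1.3.1, a drug holiday of more than 30 days for pruritus leads to permanent discontinuation of investigational product. No worsening is needed to reach that point.

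**Step 2: is it a TEAE?** It was present before first dose, so it is not new. It has not worsened, so it fails protocol 14.1.1.3 and SAP 10.2.1. Its start date is known, so the missing-date rule does not apply. It is not a TEAE. (Had it resolved and then recurred after first dose, the recurrence would be a new event and would count.)

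**Step 3: where does it appear?**

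| Output | Shown? |
|---|---|
| TEAE tables by SOC/PT, severity, relationship (SAP 10.2.3) | No |
| Pruritus AESI table, a subset of TEAEs (SAP 10.2.4.1) | No |
| TEAEs leading to withdrawal or discontinuation (SAP 10.2.3) | No |
| Disposition, with reasons (SAP 6) | Yes, as a discontinuation; SOC/PT, grade and relationship are not specified |
| AE and AE-withdrawal listings (SAP 10.2.3) | Yes, if it was entered as an AE |
| Pruritus history and medical history (SAP 7.2, 8) | Entry status only, not course on the FDC |
| Laboratory summaries and shifts (SAP 10.3) | Not for itch; a laboratory-based event would still show |

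The listing row is conditional for a reason. AE collection starts at consent to this study, and protocol 9.7.2.1 asks for pretreatment AEs after consent. Neither document says whether an ongoing parent-study event goes on the AE form or into medical history.

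**Step 4: scale.** Let *c* be the number of subjects with a persisting, non-worsening carried-in event. The documents do not give *c*; the values below are assumptions. The share left out of the TEAE tables is *c*/133.

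| *c* (assumed) | 1 | 3 | 5 | 10 | 20 |
|---|---|---|---|---|---|
| *c*/133 | 0.8% | 2.3% | 3.8% | 7.5% | 15.0% |

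For the withdrawal table, let *w* subjects stop for TEAEs and *k* for carried-in events. The table shows *w*/133; AE-driven discontinuation is (*w* + *k*)/133. With an assumed *w* = 5, the table shows 5/133 = 3.8%, against 6/133 = 4.5% for *k* = 1, 8/133 = 6.0% for *k* = 3, and 10/133 = 7.5% for *k* = 5. This shows how the error scales, not how large it will be.

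**Step 5: the two definitions side by side.** The protocol counts worsening in severity or frequency; the SAP counts only an increase in grade. The SAP also ties worsening to a Double-Blind period, and this open-label, single-arm study has none. Read literally, even a carried-in event that does worsen might not qualify. SAP 11 nevertheless reports no deviations from the protocol-defined analyses.

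**The case against.** A reader might infer that carried-in toxicity vanishes from all safety summaries. The documents do not support that. Disposition reasons, laboratory values and shifts, Hy's law counts, vital signs, physical examination and medical history are not restricted to TEAEs. The AE listings are drawn from all AEs. Under protocol 15.9 the DMC sees AEs leading to early withdrawal and a cumulative list of SAEs. What is missing is the event from the AE summary tables.

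A reader might also infer that the protocol expects such rollovers, or that the events are drug effects. It only permits them after a case-by-case discussion. The criterion does not require drug-relatedness, and the SAP itself calls pruritus the most common symptom of PBC. Nor can the 59% pruritus share in the retrospective OCA + fibrate cohort (protocol 5.5.1) stand in for the share here. That cohort was difficult to treat and 19% had AIH overlap, which this study excludes along with severe pruritus.

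Other points on that side are fair:
- Limiting TEAEs to this study is deliberate; the summary of changes says so.
- Events with a missing start date that end after first dose count as TEAEs, and SAP 5.2 moves some partial start dates to the first-dose date.
- The AESI sections speak of TEAEs and SAEs, which read alone could admit a serious event that is not treatment-emergent. The blanket sentence in SAP 10.2.3 points the other way.
- Baseline pruritus grade and a baseline myalgia rating are collected, and the questionnaire content is redacted, so it cannot be said that persistent itch is analysed nowhere else.

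These points limit how often the gap will bite and what can be claimed for it. They do not put a dated, non-worsening event into the withdrawal table.

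**Conclusion.** The point holds for the AE summary tables. A carried-in AE with a known start date that persists without worsening is in none of them. If it ends FDC treatment, the discontinuation is counted in disposition but not in the table of AEs leading to withdrawal. That table is then too low and may not agree with disposition.

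The direction of the error is certain; its size is not. Each affected subject is 1/133, about 0.8%, and the number affected could be small given the entry criteria and the Medical Monitor discussion. The conclusion rests on reading the TEAE restriction in SAP 10.2.3 as written. No hypothesis test is affected, because none is planned. This is a modest gap against the stated tolerability objective, and inexpensive to close.

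**What to change.** 1. In SAP 10.2.3, base the table of AEs leading to investigational product withdrawal or study discontinuation on every AE with that action taken on or after the first FDC dose. Flag each as a TEAE or as ongoing at first dose.
2. Add one table of AEs ongoing at first FDC dose by SOC, PT, grade, relationship and outcome, shown apart from the TEAE tables.
3. Instruct sites to enter parent-study AEs that are ongoing at Day 1 on the AE eCRF, with the parent-study onset date and the Day 1 grade. Without this, items 1 and 2 cannot be produced reliably.
4. Align the worsening rule in SAP 10.2.1 with protocol 14.1.1.3 (severity or frequency) and delete the references to a Double-Blind period.

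Prevalence of pruritus and myalgia by interval would be informative but is optional.

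The cost is SAP wording, one new table, one changed table and an eCRF completion instruction. No dose, visit or clinical rule changes. The drawback is that a carried-in event cannot be attributed to the FDC alone, which is why items 1 and 2 keep such events distinct from treatment-emergent ones.
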